#### *Screening for hepatic cirrhosis, renal insufficiency, and pregnancy.*

Brivaracetam treatment is not safe for those who are pregnant, have hepatic cirrhosis, or kidney dysfunction. Therefore, in order to be medically cleared to enter the study, participants must complete a fasting blood draw through their primary care clinic for analysis of blood urea nitrogen (BUN), creatinine, alanine transaminase (ALT), aspartate transaminase (AST), total bilirubin, albumin, GFR, calcium, corrected calcium, and human chorionic gonadotropin (hCG); urine hCG test will also be accepted. INR will be collected at the discretion of the participant's primary care provider if the participant is on anticoagulation or has abnormal LFTs. The blood lab report and medical clearance form will be faxed from the medical provider to the study coordinator within one month of draw. People who are menopausal and have not had a menstrual period for at least 12 months, or people who have had a hysterectomy will not be required to take pregnancy tests. We will use lab work performed clinically during any recent visit (within one month of testing) for screening labs when available. Any participant found to have renal insufficiency (GFR<60ml/minute), hepatic cirrhosis, Child-Pugh grades A, B, and C, or pregnant (positive hCG) will be considered a screen fail and will not progress in the study.

## 9.0 Vulnerable Populations

### 9.1 Vulnerable Populations:

## MEDICAL PROTOCOL (HRP-590)

PROTOCOL TITLE: Brivaracetam to Reduce Neuropathic Pain in Chronic SCI: A Pilot Clinical Trial  
 VERSION DATE: 03/18/2024

Population / Group	Identify whether any of the following populations will be targeted, included (not necessarily targeted) or excluded from participation in the study.
Children	Excluded from Participation
Pregnant women/fetuses/neonates	Excluded from Participation
Prisoners	Excluded from Participation
Adults lacking capacity to consent and/or adults with diminished capacity to consent, including, but not limited to, those with acute medical conditions, psychiatric disorders, neurologic disorders, developmental disorders, and behavioral disorders	Excluded from Participation
Non-English speakers	Included/Allowed to Participate
Those unable to read (illiterate)	Included/Allowed to Participate
Employees of the researcher	Excluded from Participation
Students of the researcher	Excluded from Participation
Undervalued or disenfranchised social group	Included/Allowed to Participate
Active members of the military (service members), DoD personnel (including civilian employees)	Included/Allowed to Participate
Individual or group that is approached for participation in research during a stressful situation such as emergency room setting, childbirth (labor), etc.	Excluded from Participation
Individual or group that is disadvantaged in the distribution of	Included/Allowed to Participate

## MEDICAL PROTOCOL (HRP-590)

PROTOCOL TITLE: Brivaracetam to Reduce Neuropathic Pain in Chronic SCI: A Pilot Clinical Trial  
VERSION DATE: 03/18/2024

social goods and services such as income, housing, or healthcare.	
Individual or group with a serious health condition for which there are no satisfactory standard treatments.	Targeted Population
Individual or group with a fear of negative consequences for not participating in the research (e.g. institutionalization, deportation, disclosure of stigmatizing behavior).	Excluded from Participation
Any other circumstance/dynamic that could increase vulnerability to coercion or exploitation that might influence consent to research or decision to continue in research.	Excluded from Participation

### 9.2 Additional Safeguards:

This project aims to research an intervention that may help vulnerable adults with spinal cord injuries with severe neuropathic pain, a severe health condition, and non-English speakers. To provide additional safeguards to protect individuals that may be vulnerable we:

- Will provide assurance of confidentiality, freedom to decline to participate, right to withdraw at any time without penalty.
- Engaged the SCI community in the planning of this proposed research.
- We have assessed the permissibility of the physician-investigator to obtain consent for research.
- We will emphasize the risks and demands of this study participation to potential participants.
- We will provide consent forms and a translator to individuals who are unable to read or speak in English.
- Groups included in the research where participant status in the group might be unknown (Incidental enrollment), as group status is not solicited by the research team (ex: military status, if study teams don't ask and it doesn't impact the research):

The vulnerable population groups that are allowed to participate will not be identified and information will not be collected as to a patient's vulnerable population status. This research does not add risk to this group.

## MEDICAL PROTOCOL (HRP-590)

PROTOCOL TITLE: Brivaracetam to Reduce Neuropathic Pain in Chronic SCI: A Pilot Clinical Trial  
VERSION DATE: 03/18/2024

### **10.0 Local Number of Participants**

#### **10.1 Local Number of Participants to be Consented:**

30 participants are expected to be screened. 20 participants will be enrolled at UMN.

### **11.0 Local Recruitment Methods**

#### **11.1 Recruitment Process:**

We anticipate screening 30 individuals with SCI to recruit and enroll 20 participants. The UMN healthcare system treats hundreds of patients with SCI each year. Given the large pool available for recruitment, we anticipate no difficulty in recruiting sufficient numbers of persons with SCI who meet the inclusion/exclusion criteria. Recruitment material will accurately reflect the study and will not be coercive.

*For self-referrals from recruitment materials:*

Participants may self-refer if they become aware of the study through recruitment materials, clinicaltrials.gov (or similar websites), or word of mouth referrals. A study-specific webpage will be published ([www.z.umn.edu/SCIPain](http://www.z.umn.edu/SCIPain)). A link to a RedCAP online survey will be shared for individuals to indicate their interest and preferred contact method. Participants will self-enter their contact information prior to consent for contact purposes only.

Potential participants will be identified by the Co-Principal Investigators from among patients under their care and their colleagues. Potential participants will be asked about their interest in the study at the time of a routine care visit. The patient will be given the choice, if interested, to be approached by the investigator in person, over phone or e-mail or have them reach out to the investigator. A flier or recruitment card about the study may be sent to potential participants, asking them to contact the study coordinator if they are interested.

Individuals who respond to the recruitment materials will be taken through a phone screening questionnaire with the study coordinator. If following the phone screen, the potential participant is eligible and interested; the study coordinator will schedule the screening study visit.

*Regional Healthcare Institutions:*

Contacts at regional healthcare institutions that have partnered with the University of Minnesota in previous SCI research will be made aware of this research, including the VA. Flyers and/or postcards/recruitment cards will

MEDICAL PROTOCOL (HRP-590)

PROTOCOL TITLE: Brivaracetam to Reduce Neuropathic Pain in Chronic SCI: A Pilot Clinical Trial  
VERSION DATE: 03/18/2024

be posted around campus, at the VA, on the UMN website (e.g. Brain Body Mind Lab website) and on social media with information about this study.

*Patient Representative Organizations (PRO):*

Recruitment information about this study will be provided to PRO's that will include sample text and flyers so they may distribute information about this study to their participating community members living with SCI. PRO's commonly use social media, newsletters, and share information at peer support groups to distribute information about the clinical trial. Targeted PRO's will include, but not limited to Get Up Stand Up to Cure Paralysis, Minnesota Spinal Cord Injury Association, and Morton Cure Paralysis.

MN SCI Model System Members: Like above, participants may be told about this clinical trial by their clinicians and other personnel at healthcare centers (MHealth/Fairview, Allina Health Courage Kenny Rehabilitation Institute and HealthPartners/ Regions Hospital, Hennepin Healthcare, and Mayo Clinic) that specialize in the care and wellbeing of individuals with SCI.

University of Minnesota Spinal Cord Injury Research Recruitment Registry:

We will utilize the Spinal Cord Injury Research Recruitment Registry managed by the UMN Department of Rehabilitation Medicine to help facilitate enrollment. We will filter individuals in the registry based on inclusion/ exclusion criteria and contact them via email about this research opportunity.

Online Clinical Trial Registries: This clinical trial will be listed on [www.clinicaltrials.gov](http://www.clinicaltrials.gov), [www.scitrials.org](http://www.scitrials.org), and other similar websites that assist community members to find and contact information about clinical trials.

Local Community Presentations: The study team may hold presentations (digital or in-person) about this research and other projects and research results which may inform community members about this clinical trial which may result in recruitment.

Social Media: Digital media may be shared on different social media platforms to notify potential participants about the clinical trial and how to contact the study team.

## MEDICAL PROTOCOL (HRP-590)

PROTOCOL TITLE: Brivaracetam to Reduce Neuropathic Pain in Chronic SCI: A Pilot Clinical Trial  
VERSION DATE: 03/18/2024

*Fairview Recruitment Mailings:* We will work with Fairview Research Recruitment Services to identify individuals with SCI in the overall MHealth Fairview Healthcare system and send recruitment MyChart announcements and recruitment mailings through the mail, pending approval from the Fairview Research Administration. Patients of [name] will be pre-screened using their medical chart and sent a letter in the mail if they meet eligibility criteria. Patients who have opted out of having their records used for research will not be included.

### 11.2 Identification of Potential Participants:

Participants will be identified from the clinical partnerships listed in section 11.1. Study PI and physicians from our clinical partnerships will identify potential participants from their patient pools. These physicians have access to potential study participants' medical records and knowledge of their health history. A study coordinator will contact individuals for prescreening over the phone or in-person to confirm eligibility at each site.

#### *Approaching potential participants in clinic:*

Potential participants will be identified by the principal investigator and co-investigator ([name] and [name]) and their team from among patients under [name] team's care and that of their colleagues who have legitimate access to their medical records. Through BPIC involvement EPIC will be searched on the hits provided by BPIC. If eligible a mailing will be sent out.

#### *Participants self-referred from recruitment materials:*

Potential participants will self-identify in response to flyer announcements via professional associations or support groups/word to mouth or other means.

Through BPIC involvement EPIC will be searched on the hits provided by BPIC. If eligible a mailing will be sent out.

We will use following approaches to identify participants through self-referrals:

- Postings on StudyFinder, a website managed by the UMN CTSI's Recruitment Center
- Postings on clinicaltrials.gov
- Identification via UMN's Research Match, an electronic volunteer recruitment registry

## MEDICAL PROTOCOL (HRP-590)

PROTOCOL TITLE: Brivaracetam to Reduce Neuropathic Pain in Chronic SCI: A Pilot Clinical Trial  
VERSION DATE: 03/18/2024

- Postings, flyers, or recruitment cards at the University of Minnesota and local rehabilitation centers; relevant websites and on professional social media sites (e.g., Facebook).

### *11.3 Recruitment Materials:*

The following recruitment materials will be used in this study: flyers or recruitment cards.

### *11.4 Payment:*

Participants will receive up to \$350 for their time, effort, and to assist with transportation. Participants will receive \$150 after baseline testing (Visit 2), \$150 after end of study testing (Visit 3) and \$50 after 1-month follow up testing (Visit 4).

## **12.0 Withdrawal of Participants**

### *12.1 Withdrawal Circumstances:*

At any time after enrollment, a participant may be discontinued. Reasons for discontinuation of a participant from the study will include, but may not be limited to, the following:

- The participant is found to be intolerant to a required study procedure at any time point
- Failure of the participant to adhere to protocol requirements
- The participant experiences a serious adverse experience at any time point
- The participant develops an inter-current illness that would, in the judgment of the investigator, affect assessments of clinical status to a significant degree.
- The participant enrolls in another investigational study
- The participant requests to withdraw from the study

### *12.2 Withdrawal Procedures:*

The PI and study physician will work closely with any participant wishing to withdraw from the study to ensure that the study drug is tapered appropriately and safely.

### *12.3 Termination Procedures:*

Participation may be terminated due to drug intolerance or allergy and based on clinical judgement of the study team. All data collected will be retained and analyzed unless the participant specifically requests to have their data withdrawn from the analysis.

## MEDICAL PROTOCOL (HRP-590)

PROTOCOL TITLE: Brivaracetam to Reduce Neuropathic Pain in Chronic SCI: A Pilot Clinical Trial  
VERSION DATE: 03/18/2024

### **13.0 Risks to Participants**

#### **13.1 Foreseeable Risks:**

There is a risk of drug intolerance including allergy, suicidal behavior and ideation, somnolence and fatigue, psychotic symptoms, irritability, depression, loss of coordination/balance, constipation, aggressive behavior, and anxiety. All participants and caregivers will be educated to notify the PI or a health care provider if mood changes or suicidal behavior are observed. There is the risk of lowered seizure threshold for rapid drug withdrawal without tapering. There is some discomfort with venipuncture and there is the possibility of swelling and bruising at the site. There is also a slight chance that individuals become dizzy or faint. There are potential risks of loss of privacy and confidentiality. All participants will be encouraged to contact the study coordinator, or an investigator regarding any side effects or adverse events that occur.

#### **MRI risks**

There are minimal risks or side effects of MRI testing for participants who do not have medical devices or implants. These risks include magnetic objects being turned into projectiles by the MRI, claustrophobia in the scanner, and hearing damage if hearing protection is not worn in the scanner.

#### **Venipuncture**

There is some discomfort with venipuncture and there is the possibility of swelling, inflammation, and bruising at the site, and, in rare cases, the risk of infection. There is also a slight chance that individuals become dizzy or faint. All blood draws completed at the study site will be performed by a trained technician at the UMN in the Fairview Clinical Research Unit (CRU), following standard clinical protocols to minimize risks.

#### **Risks Associated with Breach of Confidentiality**

There is a risk of breach of confidentiality. Multiple measures will be taken to minimize this risk. All information that could be used to identify a participant will be kept in secure and locked space with accessible only by the trained study coordinator and the principal investigator. All of these documents will be kept in locked file cabinets, in locked offices, at all times. Also kept secure and separate from other files will be the unique ID code number for each participant. Information collected will be stored on Box Secure Storage or REDCap. The computers used are password-protected and will only be used by trained study staff and for study purposes only. All blood samples are uniquely coded by number and are “de-identified.” Blood samples collected to test for biomarkers will be stored behind locked

## MEDICAL PROTOCOL (HRP-590)

PROTOCOL TITLE: Brivaracetam to Reduce Neuropathic Pain in Chronic SCI: A Pilot Clinical Trial  
VERSION DATE: 03/18/2024

doors in on-site freezers for an indefinite period of time with only coded numbers as key to identity. The key to the codes will be available only to selected investigators. Participants wishing to withdraw their samples from the study may do so at any time by notifying the investigators in writing. There is also a small chance that, if participants engage in a videoconference through the Zoom for Healthcare platform, the Zoom session could be hacked.

### **Participant monitoring**

Study staff will monitor and respond to reports regarding adverse events collected during sessions and on self-report questionnaires. Adverse events will also be assessed once per week throughout the study over the phone and entered into a REDCap form. Participants will also be instructed to contact the investigators and/or study staff if they experience a serious adverse event. If an event occurs, protocols for adverse event classification and reporting will be followed.

### **Participant confidentiality**

Procedures are in place for maintaining the full confidentiality of all information collected. Participant confidentiality will be protected by securing all hard copy study files in locked filing cabinets. Electronic files containing personal identifiers will be stored on Box Secure Storage or REDCap. All study staff receive training on privacy standards for maintaining participant confidentiality. All published reports will be of summary nature and no individual participants will be identified beyond the investigative staff involved in the project. Electronic data management is described above (see 'Data Coordination').

#### **13.2 Reproduction Risks:**

##### **Pregnancy**

We are excluding pregnant or lactating people from this study.

#### **13.3 Risks to Others: N/A**

## **14.0 Potential Benefits to Participants**

### **14.1 Potential Benefits:**

Because this study will be used to develop clinical trials testing pharmacological interventions to treat neuropathic pain in SCI, there is a potential future benefit to the spinal cord population.

## **15.0 Statistical Considerations**

## MEDICAL PROTOCOL (HRP-590)

PROTOCOL TITLE: Brivaracetam to Reduce Neuropathic Pain in Chronic SCI: A Pilot Clinical Trial  
VERSION DATE: 03/18/2024

### *15.1 Data Analysis Plan:*

For aim 1, the main outcome variables of interest include various dimensions of pain, mood (PHQ-9), life satisfaction (SWLS), resting state brain connectivity, and community integration (CHART-SF) measured at baseline and again at 3-months of treatment. Of particular interest is whether there is a difference in pain reduction from baseline to end of study between the treatment and control groups; this will be analyzed in this pilot with linear regression including terms for group and time and the interaction of group by time. We note that many of these instruments have bounded scores and we will include analyses that recognize these (via, e.g., non- linearities or recognize the bounds such as Tobit regression) Further exploratory analyses will examine the relationships (correlations) between changes in pain and changes in mood, life satisfaction, resting state brain connectivity, and community integration using linear regression.

For aim 2, we will use the same analytic approach we have refined in our 2 active rsfMRI studies. MRI data will be analyzed using the SPM12 based Conn toolbox 3 (Version 17f, Matlab R2018b). Preprocessing steps include realignment and unwarping, slice-timing correction, ART based identification of outlier scans for scrubbing, segmentation and normalization to MNI space, and 8 mm smoothing. Denoising steps include scrubbing, aCompCor, ICA-based denoising, Global Regression, and 0.008 to 0.09 Hz band-pass filtering). Three main comparisons will be evaluated: The effect of drug treatment on rsfMRI measures, the effect of pain intensity on rsfMRI measures (each via linear regression as in Aim 1), and the differences in rsfMRI measures between active drug responders and non-responders; this last will also be analyzed via linear regression; note, however, that this will be limited to those in the active group and people in the placebo group will not be included. First, we will evaluate region-of-interest (ROI) based functional connectivity in a set of anatomically defined regions known to be impacted in SCI and neuropathic pain: the periaqueductal gray, the bilateral thalamus, the amygdala, the hippocampus, the insula, anterior cingulate, the precentral and the post-central gyrus. Second, we will evaluate, on a voxel-by-voxel basis, amplitude of low frequency fluctuations (ALFF) and intrinsic resting state functional connectivity.

For aim 3, we will analyze miRNA expression profiles for raw cycle threshold (Ct) values using real-time Statminer software (Integromics, Inc) to identify significantly altered miRNAs. For relative quantification of miRNAs between placebo and brivaracetam-treated samples, the following

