### 1.0 Objectives

#### 1.1 Purpose:

SCI is associated with severe neuropathic pain that is often refractory to all pharmacological intervention. Our preliminary data suggest brivaracetam is a mechanism-based pharmacological intervention for neuropathic pain in SCI. In this project we will conduct a randomized, placebo-controlled pilot clinical trial to assess feasibility of a 3-month treatment course with brivaracetam. We will assess changes in pain intensity and periaqueductal gray hyperactivity. We will assess baseline periaqueductal gray hyperactivity and microRNA levels as potential biomarkers of response to treatment. We will use these preliminary findings to design larger clinical trials to establish efficacy of brivaracetam to treat neuropathic pain in SCI. The pilot data are necessary to adequately power the larger clinical trial based on SCI-specific data for each outcome of interest. Here we will be able to present the scientific evidence base supporting the rationale for this project.

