### **3.0 Study Endpoints/Events/Outcomes**

#### **3.1 Primary Endpoint/Event/Outcome:**

Our primary endpoints will be 1) safety as determined by number of drug related adverse events and assessed through weekly adverse event screening by phone, and 2) efficacy as determined by reduction in pain intensity assessed by the Brief Pain Inventory. We will use the clinically meaningful reduction in Brief Pain Inventory score of 1 point or more as the definition of “drug response” in this study.

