## 5.0 Procedures Involved

### 5.1 Study Design:

This is a multi-center randomized, double-blinded placebo-controlled pilot clinical trial. Each site (Swedish Medical Center/Craig Hospital, UMN) will enroll and study 20 adults, 18 years of age and older with SCI. [name] will serve as PI, and [name] will serve as Co-I at UMN (local site). MRI data analysis will be conducted by [name] (Harvard University). [name] will receive a deidentified dataset and will have no human subject interactions. Research activities at the Swedish Medical Center/Craig Hospital will be conducted under a separate IRB protocol at Craig Hospital.

Participants who meet the eligibility criteria will be randomly assigned to active drug (escalating brivaracetam dose to 100 mg twice daily for 3 months) or placebo based on a randomization schedule developed by our biostatistician. This is a simple computer generated 1:1 scheme that randomly assigns participants to arm A or arm B. Study participants, research coordinators, and study personnel involved in outcomes assessments and analyses will all be blinded. The drug will be provided by RxArtisans pharmacy in Wayzata, MN. The active and placebo capsules will have identical appearance and consistency. Treatment assignment will be known only to the investigational drug pharmacies (RxArtisans). We have registered this pilot study with National Institutes of Health (NIH) clinical trials registry, [www.clinicaltrials.gov](http://www.clinicaltrials.gov) (NCT04379011). The pilot data generated by this effort will be used to power a subsequent multi-center clinical trial.

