7.2.3 Future analysis of genotypes: N/A

## 8.0 Study Population

### 8.1 Inclusion Criteria:

- 18 years of age or older
- Completed inpatient rehabilitation and living in the community
- Ongoing severe below-level neuropathic pain (daily average 9/10 or 10/10)
- Tried and failed to achieve adequate pain relief with the use of other drugs (previous pain management drugs failed to decrease their pain below a self-reported level of 9 out of 10)

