### 15.2 Power Analysis:

Part of the goal of this pilot study is to obtain information that can be used for formal sample size estimation, including effect sizes and standard error estimates; therefore, analyses are included here that may not be included in a non-pilot follow-up (including the randomization analyses described below); further, some of the analyses here are exploratory to help in the design of a follow-up study. Also, (1) robust standard errors will be used in all cases to help guard against the effects of heteroskedasticity; (2) although there are a number of outcomes and, therefore, analyses, no adjustments for multiple comparisons will be made in this pilot study as the prime aim is not the level of statistical significance but rather the estimation of results needed for planning a follow-up. Of course, when disseminating our findings we will report the number of tests performed and the actual p-values so that readers can make their own adjustments if wanted.

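### The pain regression names no link between a participant's two scores, so fitted as written its standard error, a stated planning output, is too large if those scores are positively correlated

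*Combined protocol and SAP*

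**What the plan says.** The efficacy endpoint in section 3.1 is "efficacy as determined by reduction in pain intensity assessed by the Brief Pain Inventory". Section 15.1 takes scores at baseline and at 3 months, and its question of interest is "whether there is a difference in pain reduction from baseline to end of study between the treatment and control groups". On method it says that "this will be analyzed in this pilot with linear regression including terms for group and time and the interaction of group by time". For this comparison it names no participant effect, within-person covariance, clustering, change score or baseline covariate. Changes in scores appear only in the exploratory correlation analyses that follow.

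Section 15.2 adds that "robust standard errors will be used in all cases to help guard against the effects of heteroskedasticity". It also says that part of the pilot's goal is to obtain "information that can be used for formal sample size estimation, including effect sizes and standard error estimates". Section 1.1 states: "The pilot data are necessary to adequately power the larger clinical trial based on SCI-specific data for each outcome of interest". Section 5.1 says the same of the next study: "The pilot data generated by this effort will be used to power a subsequent multi-center clinical trial".

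For Aim 2, section 15.1 specifies the drug effect on the resting-state imaging measures by linear regression in the manner of Aim 1. It gives no between-arm model for PHQ-9, SWLS or CHART-SF.

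**The concern.** A model with a main effect of time needs two rows per participant. Ordinary regression on those rows treats them as independent, so the variance of the group-by-time term ignores the covariance between a person's two scores. Heteroskedasticity-robust errors allow the rows to differ in variance, but they still treat the rows as uncorrelated.

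The estimated effect and the type I error rate are not what is at risk. What is at stake is the width of the interval and the standard error handed on to the follow-up trial. In a pilot whose stated purpose is to produce planning figures, that standard error is a deliverable.

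**Working it through.** The plan gives no SD, correlation, power or standard error for these scores, so there is no figure of its own to reproduce. All SDs and correlations below are assumptions.

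**Formula.** Let n be the number per arm, s0 and s1 the baseline and 3-month SDs, and rho the pre-post correlation.
- Variance of the group-by-time term with rows treated as independent: (2/n)(s0² + s1²).
- True variance with paired scores: (2/n)(s0² + s1² − 2·rho·s0·s1).
- Ratio of standard errors: sqrt[(s0² + s1²)/(s0² + s1² − 2·rho·s0·s1)].

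The ratio does not depend on n, so it is the same whether the trial has 20 participants in all (section 23.1) or 20 per site (section 5.1). At rho = 0 it is 1. At negative rho the standard error would be too small (0.88 at rho −0.3 with equal SDs).

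**BPI average pain.** Section 8.1 requires a daily average of 9 or 10 out of 10, so s0 is at most about 0.5 if baseline scores stay in that range. The unrestricted SD is assumed to be 2 to 2.5 (section 2.2 reports 2.5 for VAS pain in an SCI sample). Selection on a narrow baseline also shrinks rho: restricted rho = rho·u/sqrt(1 − rho² + rho²u²), with u = 0.5/2 or 0.5/2.5.

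Example with unrestricted SD 2 and rho 0.5: restricted rho = 0.125/sqrt(0.75 + 0.0156) = 0.14 and s1 = 1.75. The ratio is sqrt[3.3125/(3.3125 − 0.25)] = 1.04.

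| Unrestricted rho | Restricted rho | SE too large by |
|---|---|---|
| 0.3 | 0.06-0.08 | 1-2% |
| 0.5 | 0.12-0.14 | 3-4% |
| 0.7 | 0.19-0.24 | 5-8% |

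Simulated rounded 0-10 scores, selected at 9-10, gave 2-10% with unrestricted means of 5-6, and at most 12% (mean 7, rho 0.7).

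**Another BPI score.** Section 5.2 describes worst, least, average and present pain, and the plan does not say which is primary. If the score used has s0 = 1.0:
- s1 = 2, rho 0.3: sqrt(5/3.8) = 1.15.
- s1 = 1.5, rho 0.5: sqrt(3.25/1.75) = 1.36.

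**Aim 2.** With equal SDs and no restriction at baseline the ratio is 1/sqrt(1 − rho): 1.20, 1.41 and 1.83 at rho 0.3, 0.5 and 0.7.

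**Do the robust errors help?** In simulation (equal SDs of 1, rho 0.5, 10 per arm) the true sampling SD was 0.45. The ordinary and the heteroskedasticity-robust standard errors were both 0.63, and the participant-clustered one was 0.45.

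**Effect on tests at 10 per arm** (nominal 5%). Power is for a 1.5-point effect, as written against clustered.
- Average pain: type I error as written 3.7-5.3%; power differs by −2 to +3 points.
- Baseline SD 1.0: type I error 1.1-2.7%; power 29% against 36% (SDs 1/2, rho 0.3) and 42% against 66% (SDs 1/1.5, rho 0.5).

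**Follow-up size per arm** if planned from this standard error (1-point difference, 80% power, two-sided 5%): n = 2 × 7.85 × V, where V is s0² + s1² as written and s0² + s1² − 2·rho·s0·s1 when paired.

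| s0, s1, rho | As written | Paired |
|---|---|---|
| 0.5, 2, 0.06 | 67 | 65 |
| 0.5, 1.5, 0.24 | 40 | 34 |
| 1, 2, 0.3 | 79 | 60 |
| 1, 1.5, 0.5 | 52 | 28 |

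**The case against.** The best defence is that pairing is implied. The endpoint is a reduction, drug response is a fall of at least 1 point, and both require each person's change to be computed. An analyst would probably pair, and a planner with the data could use the SD of change. This is plausible, but the endpoint wording fixes what is estimated, not how its standard error is computed, and the plan does not say that the SD of change will be reported. Section 15.2 also mentions randomization analyses. They might give valid p-values, but they are not described in the text that follows and would not alter the regression's standard error.

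A second defence is that the effect on average pain is negligible. This largely stands. With the mean of 3.0 and SD of 2.5 reported in section 2.2, rounded scores selected at 9-10 give only 1.6%, 3.2% and 6.3% at unrestricted rho of 0.3, 0.5 and 0.7. With 10 to 20 per arm, sampling error in the pilot's own SD is larger than that. The 15-36% case rests on SDs that no section supports, and it depends on which BPI score is used.

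A reader might also infer that the 20-83% figures apply to PHQ-9, SWLS and CHART-SF. The documents do not support that. The sentence with the model concerns pain, and the only stated analysis of those scales relates their changes to changes in pain, which already works within person.

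**Conclusion.** The omission and its direction are certain; the size is not. Fitted as written with complete data, the pain model gives the right estimate and a standard error that is too large for any positive correlation, and the stated robust errors do not correct it. On the assumptions shown, the excess is about 1-10% for BPI average pain, which is minor. It is 15-36%, which is moderate, only if the BPI score used has a baseline SD of 1.0, a 3-month SD of 1.5-2 and a correlation of 0.3-0.5.

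The gap extends to the Aim 2 drug-effect comparison if that model is fitted literally, at 20-83% for unrestricted measures with equal SDs and rho 0.3-0.7. How the imaging software will be set up cannot be seen, so this part is conditional. No error is claimed for PHQ-9, SWLS or CHART-SF. A reader might take the point to mean a biased effect or excess false positives, but for positive correlation the error runs the other way: intervals too wide, tests conservative, and a follow-up trial somewhat too large if sized from this figure.

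**What to change.** In section 15.1, name the link between the two scores. Any one of these is enough:
- regress the 3-month pain score on arm and the baseline value of the same score, one row per participant, with robust standard errors;
- keep the group-by-time model, with standard errors clustered on participant and a small-sample correction;
- keep the group-by-time model, with a participant random effect.

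State the same link for the Aim 2 drug-effect model and for any between-arm comparison of other pre-post scores. For planning, report the baseline and 3-month SDs, the SD of change and the pre-post correlation for each such outcome. The cost is a few sentences in the analysis plan, with no new data and no extra participants. Enrolment is recorded as complete in the revision history, but that does not prevent a clarification of the analysis text.
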